Aim 1.1 Targeted Approach: We will determine cross-sectional and longitudinal changes of ceramides, acylcarnitines, BCAA, and a biomarker panel for CVD outcomes and their relationship with stress hyperglycemia (BG >140mg/dl on ICU arrival). Path-specific biomarkers include: TNF- α and C-reactive protein (inflammation), fibrin degradation products (pro-thrombosis), heat shock protein-70 (cell stress), and suPAR (immune modulation and inflammation). Counterregulatory hormones include: cortisol, glucagon. Glucose, insulin and indexes of insulin sensitivity/insulin resistance: will be derived from glucose, insulin and c-peptide values. **Methods:** Plasma samples will be stored at -80°C until analysis. Serum CRP and FDP including fragments D and E, D -dimer, and additional intermediate cleavage products will be determined (FirstMark, San Diego, CA). Serum HSP-70 will be measured with a sandwich enzyme-linked immunosorbent assay (R&D Systems, Minneapolis, MN). Plasma suPAR levels will be measured using commercially available kits (suPARnostic kit; Virogates, Copenhagen, Denmark). Minimum detectable CRP, FDP, HSP-70, and suPAR have been reported at 0.1 mg/L, 0.06 $\mu\text{g}/\text{mL}$, 0.313 ng/ml, and 0.1 ng/ml, as described previously.⁶⁵⁻⁶⁸ Liquid chromatography tandem mass spectrometry techniques will be used to quantitatively profile ceramides, acylcarnitines, branched chain amino acids (leucine, isoleucine, valine), and aromatic amino acids (tyrosine and phenylalanine) in plasma samples along with standard reference samples. Glucose levels will be analyzed by the hexokinase method (Beckman-Coulter, Los Angeles, CA). Counterregulatory hormones, insulin, C-peptide levels by two-site sequential chemiluminescent immunometric assays. Surrogates of beta cell function (HOMA-B) and insulin resistance (HOMA-IR) will be derived from fasting glucose, c-peptide and insulin.

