Analysis: Student's t test and χ^2 tests will be used when appropriate. Mann-Whitney U or Kruskal-Wallis nonparametric tests will be used for non-normally distributed variables. Analysis will account for age-matching. The relationship between biomarkers and stress-hyperglycemia and surrogates of insulin sensitivity and beta cell function will be determined using the Cox proportional hazards regression in unadjusted models and in models adjusted by gender, and smoking status to evaluate the impact of each 1 U increase in a biomarker risk score based on previously defined cut points for CRP, FDP, HSP-70, and suPAR (3 mg/L, 1.0 $\mu\text{g}/\text{mL}$, 0.313 ng/ml, and 3.5 ng/ml, respectively) as previously described.^{65,66,68}

1.2 Untargeted Analysis: Utilizing untargeted LCMS-derived high-resolution metabolomics (HRM) analysis we aim to identify additional candidate metabolites and new metabolic pathways associated with incident stress hyperglycemia during cardiac surgery. **Methods:** HRM analysis is a major component of my career development plan. Data analysis will be conducted under the supervision of [name]. Data Interpretation will be conducted under the guidance of [name] (expert in metabolism). I will also have local support from [name] for interpretation of metabolomics results, as well as statistical support from [name]. [name] will provide guidance for hands-on use of metabolomics tools. Co-mentors and collaborators are experts in the data management requirements of the LCMS-derived high-resolution metabolomics (HRM) analysis proposed in this project. Serial samples will be collected: at baseline (up to seven days before surgery), at 15 minutes (after cardiac bypass has started for on pump surgeries) or 2hrs after sternum incision (for off pump surgeries), 24hrs, 72-96hrs and 30 days after surgery. Plasma samples will be stored at -80°C until analysis. The methods use UPLC with ultra-high resolution mass spectrometry with a dual chromatography, dual ionization approach with each sample being analyzed with three technical replicates.¹²²⁻¹²⁴

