Inform consent and randomization: Patients will be consented during the preoperative evaluation on admission at least 24-72 hours prior to scheduled surgery. The investigators or study coordinators will review and explain the contents of the informed consent document to the eligible patient. Additional details are outlined in the Human Subjects section.

Study Sites: This pilot study will be conducted at Emory University Hospital, Emory Midtown Hospital, and Grady Memorial Hospital, Atlanta.

ICU Stay: Study patients who develop stress-hyperglycemia ($BG > 140$ mg/dl) in the ICU will be started on intravenous CII adjusted to maintain a BG target between 100-140 mg/dl following a standard hospital protocol.

Transition from ICU to Regular Floor: Patients with fasting and/or premeal $BG > 140$ mg/dl will receive coverage with sliding scale insulin (supplements), those with 2 consecutive $BG > 180$ mg/dl, or average daily $BG > 180$ mg/dl will be started on rescue therapy with SC basal insulin (glargine or levemir) once daily.¹¹¹

Rescue Therapy with Basal Insulin in Non-ICU Settings¹¹¹:

- BG between 140-200 mg/dl= start basal insulin at 0.1 units per kg weight per day.
- BG between 201-400 mg/dl= start basal insulin at 0.2 units per kg weight per day.
- Basal insulin will be given once daily, at the same time of the day.

Insulin adjustment and supplemental (correction) insulin: we will use a standard insulin treatment protocol.^{4,86}

Investigational drugs:

- Dulaglutide injection: 0.75 mg/0.5 mL solution in a single-dose pen will be provided to patients
- Saline injection/0.5 mL pre-drawn solution, a tuberculin syringe will be provided to patients
- A research pharmacist at the site-specific Clinical Research Network Unit will provide dulaglutide and saline. Patients will be instructed on self-injection technique.

Withdrawal Criteria (please see additional details in Human Subjects and DSMP sections):

- The subject may withdraw at any time during the study by primary care provider or research team.
- The subject may be withdrawn at the investigator's discretion due to a safety concern or for contravention to the inclusion and/or exclusion criteria.
- Subject diagnosed with acute pancreatitis by clinical and/or radiographic criteria.

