Analysis: The primary endpoint of Aim 2 is the frequency of stress-hyperglycemia ($BG > 140$ mg/dl) requiring insulin therapy during the postoperative period (Aim 2.1). We will use two-sided Chi-square test or Fisher's exact test for the primary outcome. In Aim 2.2 we will compare the difference in mean BG upon ICU arrival and the frequency of rescue therapy with SC insulin after transition to regular floor. We will also explore differences in complications between groups. Secondary outcomes of interest can be a binary outcome (e.g. whether CII is needed in ICU), or a count outcome (e.g. number of perioperative complications), or a continuous outcome (e.g. mean ICU BG concentration). We will adopt the same strategy proposed for the primary outcome to analyze any binary secondary outcomes. For secondary outcomes measured as counts, we plan to use nonparametric tests such as Krustal-Wallis tests. Univariate Poisson regression (or Negative Binomial regression) will be performed to estimate the marginal treatment effect. In addition, we will also conduct multivariate Poisson regression (or Negative Binomial regression) to assess the outcome differences between the two study groups with potential confounders considered. For secondary endpoints that produce continuous outcomes, we will use two-sample t-tests or nonparametric Wilcoxon tests to compare study groups.

Transformations will be applied if normality violation is detected.

Aim 2.3. To compare changes in metabolites and biomarkers in response to dulaglutide or placebo (measured in Aims 1.1 and 1.2), as well as beta-cell function and insulin resistance estimates.

Methods: Biomarkers and assessment of candidate metabolites will follow the same procedures as specified in Aim 1. Surrogates of beta cell function and insulin resistance will be derived from glucose, insulin, and c-peptide measurements acquired during the perioperative period.

[figure not shown]

Figure 8. Treatment groups in Aim 2. Patients will be assigned to receive dulaglutide or placebo 1-3 days before surgery.

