Analytic Techniques: Glucose levels will be analyzed by the hexokinase method (Beckman-Coulter, Los Angeles, CA). Insulin and C-peptide levels will be measured by two-site sequential chemiluminescent immuno-metric assays as previously described. Surrogates of beta cell function (HOMA-B) and insulin resistance (HOMA-IR) will be derived from fasting glucose, c-peptide and insulin. Only glucose and c-peptide will be measured serially after surgery (given high likelihood of exposure to exogenous insulin).

Analysis: We will integrate analyses from Aims 1 and Aims 2 to evaluate the role of dulaglutide on metabolites, metabolic pathways and biomarkers. We will use univariate and multivariate statistical methods, such as linear mixed effects models with post-hoc Tukey tests, LIMMA, and multilevel sparse Partial Least Squares Discriminant Analysis (msPLSDA), as described in Aim 1.

Expected outcomes in Aim 2: In Aim 2.1 we expect to observe a decrease in the number of patients with stress-hyperglycemia with low risk of hypoglycemia with dulaglutide therapy. We expect to find a least an 18 mg/dl (1 mmol/l) mean difference in BG between groups during ICU stay. In Aim 2.2 we don't expect to find differences in hospital outcomes. In Aim 2.3 We expect to observe differential changes in up or down regulation of metabolic pathways in response to dulaglutide compared to placebo.

Potential Pitfalls, and Possible Solutions, Alternative Consideration: Recruitment and retention of patients are important challenges in RCTs; however, Emory University and affiliated hospitals serve as cardiovascular referral center to a large population in the city of Atlanta, with over 1,000 major cardiac surgeries performed yearly. In our previous trial we recruited 340 patients over 3 years, therefore we expect to have enough time during the award period to complete enrollment (please see research timeline). It is possible that dulaglutide does not have an effect on the prevention of hyperglycemia. This information will help us understand the contribution of the incretin pathway to glucose metabolism during surgical stress.

E. Risks to Human Subjects

E.1.1 Human Subjects Involvement, Characteristics, and Design

- Description and justification for proposed involvement of human subjects:**

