will be possible using innovative ultra-high resolution mass spectrometry (HRMS) with liquid chromatography (LC) and gas chromatography (GC) and advanced data extraction algorithms. LC-HRMS will also measure >2000 metabolomic intermediates in plasma at the time of surgery and at follow-up, providing coverage of >85% of human metabolic pathways. ***The overall hypotheses are that candidate metabolites such as: ceramides, acylcarnitines, and branched-chain amino acids (BCAAs) are associated with incident stress hyperglycemia, and that hyperglycemia leads to changes in path-specific biomarkers related to CV risk. In addition, exposure to an agent associated with low risk of hypoglycemia can positively affect the trajectory of metabolic changes during acute surgical stress.***

Baseline measurements: Samples will be collected up to seven days prior to scheduled CABG surgery. Blood samples will be processed by the CRN Laboratory and stored at -80°C until ready for batch analysis. Fasting plasma metabolomics analysis will be performed using high-resolution metabolomics (HRM) methods established in Co-mentor [name]' laboratory. Samples for measurement of biomarkers, glucose, cortisol, glucagon, insulin and c-peptide will also be collected. Indexes of insulin sensitivity/insulin resistance: will be derived from glucose, insulin and c-peptide values. Indexes of insulin secretion: pancreatic β-cell insulin secretion capacity will be assessed with HOMA-B.

Sources of materials: Research material will include medical history, demographic information, and complications obtained both from subjects, medical record, and study blood samples.

Data collected: Data to be collected is detailed in **Table 1** below, along with the source of the data. Baseline and daily information will be entered by [name] or a study coordinator into data collection paper forms and into an electronic database (REDCap) provided by the Emory Research Information Technology Department.

Table. Data to be collected and source

Data Item	Source
-Vitals (e.g. blood pressure, pulse, temperature)	Medical Exam
-Height, weight, BMI	Manual stadiometer and digital scale
-Demographic Information (e.g. age, race)	Self-report and medical records
-Medical history (e.g., comorbidities, surgeries)	Self-report and medical records
-Social history (e.g., education, smoking, alcohol use)	Self-report and medical records
-Indexes of insulin secretion, resistance and sensitivity	serial blood draws

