- Data collection and data entry. Study members will enter baseline and daily data for this study into data collection paper forms and into an electronic database provided by the Emory Research Information Technology Department. Baseline data will include demographics/history form (subject gender, date of birth, ethnicity, dates of hospitalization and operation, history of diabetes, and comorbid conditions, body weight, BMI, smoking status, type of surgery, APACHE score. Daily information will be collected on treatment (insulin IV or SC and dosage, antibiotics, use of corticosteroids), nutrition support, BG and laboratory values, hospital complications and adverse events, and length of ICU and hospital stay.

E.1.3. Potential Risks

- **Potential Risks/Discomforts:**
 - a. Venipuncture: There is some minor discomfort and risk of mild bruising during venipuncture. Standard sterile techniques will be used during phlebotomy; thus, infection is unlikely. Disposable pre-sterilized needles and syringes will be used for all blood drawing in this study; needles and syringes will not be reused. Discomforts associated with venipuncture are rapidly reversible. Approximately 40 mL of blood will be obtained for all the blood measurements proposed.

- b. Hypoglycemia: In our previous ICU studies, we observed that <10% of cardiac surgery subjects during CII and 20-30% during SC insulin experienced hypoglycemia. No episodes of severe hypoglycemia were observed during CII in our study. The use of insulin in combination with GLP1-RA may increase the risk of hypoglycemia. The number of mild (≤ 70 mg/dL) and severe hypoglycemia (≤ 40 mg/dL) and clinical consequences (neurological and cardiovascular) will be compared between groups. Treatment of hypoglycemia: hypoglycemia, defined as a BG <70 mg/dL will be treated by a standard hypoglycemia protocol available at each hospital.
- c. Hyperglycemia: it is very likely that a high proportion of patients randomized to placebo develop hyperglycemia. All subjects with hyperglycemia (in both groups) will be treated by standard protocols in the ICU units at each hospital. We expect that ~50-60% of subjects randomized to placebo will experience one or more episodes of hyperglycemia. The frequency of severe hyperglycemia will be analyzed statistically.

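### Post-operative HOMA-IR and HOMA-B are not defined consistently, and at 24 h and 72-96 h a glucose and C-peptide version cannot be separated from insulin treatment

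*Combined protocol and SAP*

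**What the plan says.** **Which analytes.** Aim 2.3, Methods: "Surrogates of beta cell function and insulin resistance will be derived from glucose, insulin, and c-peptide measurements acquired during the perioperative period". Aim 2.3, Analytic Techniques (also Aim 1.1, Methods): "Surrogates of beta cell function (HOMA-B) and insulin resistance (HOMA-IR) will be derived from fasting glucose, c-peptide and insulin". The next sentence of Analytic Techniques is "Only glucose and c-peptide will be measured serially after surgery (given high likelihood of exposure to exogenous insulin". The data table in E.1.2 gives serial blood draws as the source for the secretion and resistance indexes. At baseline all inputs exist: "Samples for measurement of biomarkers, glucose, cortisol, glucagon, insulin and c-peptide will also be collected" (E.1.2, Baseline measurements).

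**When.** Aim 1.2 schedules a baseline draw, an intra-operative draw, then "24hrs, 72-96hrs and 30 days after surgery". Aim 2.3 adopts the Aim 1 procedures for biomarkers and metabolites.

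**Insulin treatment.** D2, ICU Stay: patients who exceed 140 mg/dl in the ICU "will be started on intravenous CII adjusted to maintain a BG target between 100-140 mg/dl following a standard hospital protocol". The D2 Rationale says that most patients with stress hyperglycemia need an infusion and that about half go on to subcutaneous insulin on the ward. E.1.3: "We expect that ~50-60% of subjects randomized to placebo will experience one or more episodes of hyperglycemia".

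**Groups compared.** The expected outcomes of Aim 2 include fewer hyperglycemic patients on dulaglutide. Aim 1 defines cases by glucose above 140 mg/dl on ICU arrival. The Aim 2.3 analysis paragraph does not mention insulin exposure.

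**The concern.** HOMA is a fasting index that assumes an untreated steady state between glucose and endogenous insulin. Measuring C-peptide instead of insulin keeps injected insulin out of the assay, which is the plan's stated reason. It does not restore the steady state. In a treated patient the glucose value is partly set by the titration protocol, and exogenous insulin may also lower C-peptide.

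This would matter less if treatment were equally common in the groups compared, but it is not expected to be. If dulaglutide prevents hyperglycemia, fewer of its patients receive insulin. In Aim 1, the glucose threshold that makes a patient a case is the one that starts the infusion, so case status and insulin exposure nearly coincide. A difference in a post-operative index between arms, or between cases and controls, could then reflect who was on insulin. What is at stake is the reading of Aim 2.3 and of the longitudinal part of Aim 1.1.

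**Working it through.** The documents give no effect size, SD or formula for HOMA-IR or HOMA-B, so there is no figure to reproduce. The check has a textual part and an illustrative part.

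**1. What can be computed at each draw** (assuming the Aim 1.2 schedule applies to these analytes)

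| Draw | Insulin assayed? | Fasting and free of exogenous insulin? |
|---|---|---|
| Baseline | Yes | Fasting inputs specified; patients previously treated with antidiabetic agents are excluded |
| Intra-operative | Not stated | Not stated |
| 24 h | No | No condition set; ICU infusion possible |
| 72-96 h | No | No condition set; infusion or ward insulin possible |
| 30 days | No, if the post-surgery statement covers it | Not stated |

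An insulin-based HOMA is therefore unavailable from the serial post-operative samples, and the C-peptide alternative is not named.

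**2. How many placebo patients might be exposed.** With 30 per arm, 50-60% with at least one hyperglycemic episode is 30 x 0.50 = 15 to 30 x 0.60 = 18, leaving 12 to 15 without one. If about half of those continue subcutaneous insulin, that is 7.5 to 9 patients on the ward. These figures count patients with an episode or with continued treatment, not patients on insulin at a given draw.

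**3. What insulin could do to one patient's index.** Assumed values: glucose 160 mg/dl and C-peptide 3.0 ng/ml before infusion; glucose 125 mg/dl on infusion. The resistance-type index is glucose x C-peptide. The secretion-type index is C-peptide/(glucose - 63), where 63 mg/dl = 3.5 mmol/l x 18.

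| C-peptide on infusion | Glucose x C-peptide (before: 480) | C-peptide/(glucose - 63) (before: 3.0/97 = 0.0309) |
|---|---|---|
| unchanged, 3.0 | 375 (-22%) | 3.0/62 = 0.0484 (+56%) |
| 25% lower, 2.25 | 281 (-41%) | 2.25/62 = 0.0363 (+17%) |
| 50% lower, 1.5 | 187.5 (-61%) | 1.5/62 = 0.0242 (-22%) |

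The sign of the secretion-type change depends on C-peptide suppression, which the documents do not give.

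**4. What that could do to the arm comparison.** Suppose the drug has no true effect on the index, and insulin multiplies the index by m. With shares pD and pP on insulin at the draw, the dulaglutide/placebo ratio of geometric means is exp((pD - pP) x ln m). The documents give neither m nor pD. I take pP as 50% or 60% and assume that dulaglutide halves it.

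| m | 50% vs 25% | 60% vs 30% | equal exposure |
|---|---|---|---|
| 0.9 | 1.03 | 1.03 | 1.00 |
| 0.7 | 1.09 | 1.11 | 1.00 |
| 0.5 | 1.19 | 1.23 | 1.00 |

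For the secretion-type index, m = 97/62 = 1.56 (C-peptide unchanged) gives 0.89 and 0.87; m = 0.5 x 97/62 = 0.78 (C-peptide halved) gives 1.06 and 1.08. The spurious difference changes sign.

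**The case against.** **The authors anticipated the problem.** They drop post-operative insulin because of exogenous exposure, and they specify fasting inputs for HOMA. Both are true, and baseline HOMA stands. But the first protects only the insulin assay, and the second is not carried into draws timed by hours after surgery. Listing the indexes under serial draws also makes a baseline-only reading insecure.

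**Not every post-operative draw is under infusion.** Correct. The infusion is conditional on exceeding 140 mg/dl, 40-50% of placebo patients are expected to have no hyperglycemic episode, and the later draws may follow its end. The exposure shares above may therefore be too high for any one draw. The intra-operative draw follows dosing and precedes the ICU, and the post-surgery restriction does not cover it; its status has to be stated.

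**A stronger reading is tempting:** that no perioperative HOMA can be valid, that any dulaglutide effect on resistance would be an artefact, and that a working drug would appear to worsen resistance. The documents do not support this. A real effect is not excluded. The predicted reversal needs assumed C-peptide suppression or unequal glucose: a treated placebo patient and an untreated dulaglutide patient, both at 125 mg/dl and 3.0 ng/ml, each give 375. Dulaglutide is described as raising insulin secretion and lowering glucose, which move glucose x C-peptide in opposite directions.

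**A plain C-peptide/glucose ratio might seem a safe substitute.** It is not. On the same assumed values it moves from 0.01875 to 0.024, 0.018 or 0.012 (+28%, -4%, -36%), the same ambiguity of sign.

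**Conclusion.** The point holds in a limited form. The two Aim 2.3 paragraphs conflict on whether insulin is available after surgery. As written, the plan yields either no post-operative index or an unnamed one that, at 24 h and 72-96 h, cannot be separated from insulin treatment. A between-arm or case-control difference at those draws could be biased.

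The 0 to about 23% range for the resistance-type index rests on assumed values: exposure halved or equal, and an index lowered by 10-50% on insulin. Stronger suppression would widen it. It shows that the bias can be material and does not estimate it; the documents determine neither its size nor its direction.

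The objective is exploratory. The primary endpoint, the glycemic secondary endpoints and the baseline HOMA comparison in Aim 1 are not touched. The change should be made before analysis, but it does not threaten the trial's main result.

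**What to change.** 1. Reconcile the Aim 2.3 Methods and Analytic Techniques paragraphs, and the E.1.2 data table, on which analytes are measured at which draw, including the intra-operative and 30-day draws.
2. Limit HOMA-IR and HOMA-B to time points that are fasting and free of exogenous insulin: baseline and, if both conditions are confirmed, day 30. Name one C-peptide-based formula and use it at both. This rule selects samples for analysis; it does not ask for any change in insulin treatment.
3. At 24 h and 72-96 h, report glucose and C-peptide by randomized arm as descriptive measures, with recorded insulin use alongside. Draw no conclusion about insulin resistance from these draws, and apply the same rule to the Aim 1 case-control comparison.
4. Confirm that insulin status at the time of each draw is captured. Dose and infusion duration are recorded (Aim 2.2 endpoints; E.1.2), but status at the draw is not listed.
5. Label any breakdown by insulin use as conditioning on a post-randomization variable.

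**Cost.** Wording changes, no new samples, and possibly one added data field. The scientific price should be stated openly: Aim 2.3 will have no in-hospital post-operative estimate of insulin resistance. Day 30 does not fill the gap. With a single dose 1-3 days before surgery, it falls 31 to 33 days after dosing (30 + 1 to 30 + 3) and does not measure the perioperative drug effect.
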